## **15.2. Physical Examination**

Any clinically significant abnormal physical examination results are recorded as AEs and included in the AE listings and tables accordingly.

Slit lamp and visual acuity data will be summarized.

A subject listing of slit lamp and visual acuity data will be produced.

## **15.3. Vital Signs, Oxygen Saturation, Height, Weight**

Vital signs, including temperature (°C), systolic and diastolic blood pressure (mmHg), heart rate (bpm), and respiratory rate will be summarized using descriptive statistics, at baseline and each study day and time point by dose level in Part 1 and by tumor cohort in Parts 2A and 2B for all actively treated subjects. Oxygen saturations (%), height (cm), weight (kg), BMI (kg/m^2), and BSA (m^2) will be summarized similarly.

The following vital signs categories will also be summarized:

- Systolic pressure: for high values  $\geq 180$  and increase from baseline of  $\geq 20$ . Low values  $\leq 90$  and decrease from baseline of  $\geq 20$ .
- Diastolic pressure: for high values  $\geq 105$  and increased from baseline of  $\geq 15$ . Low values  $\leq 50$  and decrease from baseline of  $\geq 15$ .

- Heart rate: for high values  $\geq 100$  and increase from baseline of  $>25\%$ . For low values:  $\leq 50$  and decrease from baseline of  $>25\%$ .
- Body temperature: for high values  $\geq 39.1$  Celsius.

Changes from baseline will also be summarized at each post-baseline study visit.

Listings of vital signs results, oxygen saturations, height, weight, BMI, and BSA will also be produced.

## 15.4. Electrocardiogram

QT interval corrected for pulse rate by Fridericia's formula (QTcF) will be summarized using descriptive statistics at baseline and each day and time point by dose level in Part 1 (Dose escalation) and by cohort in Parts 2A and 2B (Tumor-specific Dose Expansion and Dose optimization). Shifts from baseline in ECG interpretation will be also summarized using frequency and percentages by dose level in Part 1 (Dose Escalation) and by cohort in Parts 2A and 2B (Tumor-Specific Dose Expansion and Dose Optimization).

To assess the frequency of QTc interval prolongation, the number and percentage of subjects having notable ECG values according to the following categories will also be summarized by dose level in Part 1 (Dose escalation) and by cohort in Parts 2A and 2B (Tumor-specific Dose Expansion and Dose optimization):

- Change from Baseline in QTcF:  $\leq 30$ ,  $>30$  to  $\leq 60$ ,  $>60$  msec
- Maximal QTcF:  $>450$  to  $\leq 480$ ,  $>480$  to  $\leq 500$ ,  $>500$  msec

A subject listing of ECG data will also be produced.

## 15.5. Clinical Laboratory Data

Continuous variables will be summarized by dose level in Part 1 (Dose Escalation) and by tumor cohort in Parts 2A and 2B (Tumor-Specific Dose Expansion and Dose Optimization) and for all actively treated subjects at each visit and time point (where appropriate) using arithmetic means, medians, minimum and maximum values. Categorical variables will be summarized by dose level in Part 1 (Dose Escalation) and by cohort in Parts 2A and 2B (Tumor-Specific Dose Expansion and Dose Optimization) using frequencies and percentages for all actively treated subjects at each visit and time point (where appropriate). Shift tables summarizing changes from baseline will also be produced by dose level in Part 1 (Dose Escalation) and by cohort in Parts 2A and 2B (Tumor-Specific Dose Expansion and Dose Optimization).

Unscheduled laboratory data will be included in subject listings and denoted as unscheduled. Summaries by visit will use the nominal visit value in the event of multiple laboratory values drawn within a visit window. However, all values drawn within a study window will be used to identify the minimal and maximal values. In the event that visit windows overlap, only the values from assessments occurring after the previous and prior to the subsequent nominal visit value will be considered for identification of the minimal and maximal values.

Summaries of abnormal laboratory results will be presented by analyte and severity grade.

A shift table consisting of changes from baseline in neutrophil counts will be produced.

A listing of tumor marker data will be produced. The tumor marker reference ranges are provided in [Appendix C Tumor Marker Reference Ranges](#).

## **16. PHARMACOKINETIC ANALYSES**

Details of the PK analyses are provided in a separate document.

## **17. PHARMACODYNAMIC ANALYSES**

Details of PD analyses are provided in a separate document.

## **18. INTERIM ANALYSES (EXPANSION COHORTS ONLY)**

In the tumor-specific expansion cohorts, the Go/No-Go procedure will be carried out at completion of Stage 1 based on the CBR exceeding a target value, or falling below a lower reference value. As previously noted, the following target values and lower reference values are defined as: CBR  $\geq 6.7\%$  (1/15) vs CBR  $< 6.7\%$  (1/15) for all Part 2A expansion cohorts.

The Go/No-Go criteria for the interim planning are presented in [Table 3](#).

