10.6. Interim Analyses

The Go/No-Go futility analysis for each tumor-specific cohort in Part 2A will be based on CBR as the primary outcome measurement (as defined in [Section 10.5.5](#)) after Stage 1 enrollment of 15 subjects. Each of the expansion cohorts is based on the following assumptions:

- Each expansion cohort has a maximum sample size of 35 with one interim futility analysis at 15 subjects. At the interim analysis, if there is 1 or no subject with CBR (ie, CBR rate <7%), further enrollment into the cohort will be stopped for futility. If futility is rejected at the interim analysis (ie, 2 or more of 15 subjects with clinical benefit), the final analysis will be based on a total 35 subjects (ie, 20 additional subjects evaluable for CBR). Note: Outcomes (ie, presence or absence of clinical benefit) for subjects enrolled in Part 1 with the same tumor type and who received the same dose of KZR-261 as evaluated in the corresponding Part 2A, tumor-specific cohort may be included among the initial 15 subjects at the interim analysis, as described above.

The operating characteristics of this design are presented in [Table 13](#). If the true CBR is less than 5%, there is a reasonable chance to reach the futility criterion at interim. On the other hand, if the true CBR is 20% or higher, the probability to stop for futility is moderately low (<20%).

Table 13: Operating Characteristics of Dose Expansion Phase (Part 2A)

True CBR	Interim Analysis (N=15)		Final Analysis (N=35)		
	Pr(Futility*)	Pr(obs. CBR ≥15% 6 or more subjects with CBR)	Pr(obs. CBR ≥20% 7 or more subjects with CBR)	Pr(obs. CBR ≥25% 9 or more subjects with CBR)	Pr(obs. CBR ≥25% 9 or more subjects with CBR)
5%	83%	<1%	<1%	<1%	<1%
10%	55%	11%	5%	<1%	<1%
15%	32%	39%	25%	7%	7%
20%	17%	67%	54%	25%	25%
25%	8%	86%	78%	52%	52%
30%	4%	95%	92%	76%	76%
35%	1%	98%	97%	91%	91%

CBR=clinical benefit rate; obs.=observed; Pr=probability

* 1 or fewer subjects with CBR among the first 15 subjects.

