- At the interim analysis, if there is 1 or no subject with clinical benefit (ie, CBR rate <7%), further enrollment into the cohort will be stopped for futility. If futility is rejected at the interim analysis (ie, 2 or more of 15 subjects with clinical benefit), the final analysis will be based on a total 35. Note: Outcomes (ie, presence or absence of clinical benefit) for subjects enrolled in Part 1 with the same tumor type and who received the same dose of KZR-261 as evaluated in the corresponding Part 2A, tumor-specific cohort may be included among the initial 15 subjects at the interim analysis, as described above.

The operating characteristics of this design are presented in [Table 3](#). If the true CBR is less than 5%, there is an 83% probability to reach the futility criterion at interim. On the other hand, if the true CBR is 20% or higher, the probability to stop for futility is 17%.

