**Table 3: Operating Characteristics of Dose Expansion Phase (Part 2A)**

True CBR	Interim Analysis (N=15)		Final Analysis (N=35)		
	Pr(Futility*)	Pr(obs. CBR ≥15% 6 or more subjects with CBR)	Pr(obs. CBR ≥20% 7 or more subjects with CBR)	Pr(obs. CBR ≥25% 9 or more subjects with CBR)	
5%	83%	<1%	<1%	<1%	
10%	55%	11%	5%	<1%	
15%	32%	39%	25%	7%	
20%	17%	67%	54%	25%	
25%	8%	86%	78%	52%	
30%	4%	95%	92%	76%	
35%	1%	98%	97%	91%	

CBR=clinical benefit rate; obs.=observed; Pr=probability

\* 1 or fewer subjects with CBR among the first 15 subjects.

In Part 2B (Dose Optimization), up to 120 subjects may be enrolled into up to 4 tumor-specific cohorts (30 per each tumor-specific cohort [15 per dose level]) based on the totality of data after data from Parts 1 and 2A has been assessed. The sample size for Part 2B is based on clinical considerations.

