### **7.4. Data Analysis Conventions**

All data analysis will be performed by [REDACTED] after the study is completed and the database has been locked. Statistical programming and analyses will be performed using SAS® version 9.4 or higher. Output will be provided in rich text format (RTF) for tables and portable document format (PDF) for tables, listings, and figures using landscape orientation. All study data will be listed by subject, dose level in Part 1 (Dose Escalation) and cohort in Part 2A and 2B (Tumor-Specific Dose Expansion and Dose Optimization), and visit (as applicable) based on all enrolled subjects unless otherwise specified. Listings will be sorted by dose level in Part 1 (Dose Escalation) and by cohort in Part 2A (Tumor-Specific Dose Expansion) and Part 2B (Dose Optimization), subject number, visit/time point, and parameter as applicable.

Summaries for continuous and ordinal variables will include the number of observations (n), arithmetic mean, standard deviation, median, minimum, and maximum. Minima and maxima will be reported with the same precision as the raw values; means and medians will be presented to one additional decimal place than reported in the raw values. Standard deviations will be presented to two additional decimal places than reported in the raw values. Summaries for discrete variables will include counts and percentages. All percentages will be rounded to one decimal place (ie, XX.X%). Changes from baseline will be calculated as follow-up visit minus baseline.

Unless otherwise specified, all data will be summarized by dose level and overall, for Part 1 (Dose Escalation), tumor-specific cohort for Part 2A (Dose Expansion), and dose and tumor-specific cohort for Part 2B (Dose Optimization).

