## **19. CHANGES FROM PROTOCOL-STATED ANALYSES**

There are no changes from the protocol-stated analyses.

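### SAP 18 makes 1 of 15 a Go at the Part 2A interim, where SAP 5, Table 3 and Protocol 10.6 all stop at 0 or 1 of 15

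*SAP*

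**What the plan says.** The Part 2A futility gate is described in four places.

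- **SAP 5** gives the stopping side as "if there is 1 or no subject with clinical benefit (ie, CBR rate <7%), further enrollment into the cohort will be stopped for futility" and the continuing side as "If futility is rejected at the interim analysis (ie, 2 or more of 15 subjects with clinical benefit".
- **SAP Table 3, footnote**, defines the futility event as "1 or fewer subjects with CBR among the first 15 subjects".
- **Protocol 10.6** has the same stopping count, "if there is 1 or no subject with CBR (ie, CBR rate <7" percent, and the same continuing count of at least 2.
- **SAP 18** drops the counts and gives a target value against a lower reference value: "CBR $\geq 6.7\%$ (1/15) vs CBR $< 6.7\%$ (1/15) for all Part 2A expansion cohorts". It presents these as already noted, then adds "The Go/No-Go criteria for the interim planning are presented in" Table 3.

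SAP 19 states "There are no changes from the protocol-stated analyses". SAP 1 says that the SAP's methods take precedence over the protocol's.

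**The concern.** The first three places agree that 1 of 15 stops the cohort. In SAP 18 the Go side carries the greater-than-or-equal sign with 1/15 printed beside it. One of 15 is equal to 1/15, so it lands on the Go side and only 0 of 15 is left as a No-Go. The section contradicts both the earlier text it says it repeats and the table it cites.

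This is the one result where the rule has to be exact, and it is a likely one in an inactive cohort. SAP 18 is also where someone running the interim would look first. A literal application would carry a cohort on towards 35 subjects when the rest of the plan closes it at 15. The 83% and 17% stopping probabilities quoted in SAP 5 would then describe a gate other than the one used. Because SAP 19 declares no change, nothing warns the reader.

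**Working it through.** **Inputs.** Interim n = 15 and maximum 35 per cohort, so 20 more subjects after a Go (Protocol 10.6, SAP 4.1.2 and SAP 5). True CBR values and printed probabilities are from SAP Table 3. Outcomes are taken as independent with a common probability p.

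**Step 1: reproduce the printed futility column.** Let X be the number of the 15 with clinical benefit.

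- Stop at 0 or 1: P(X ≤ 1) = (1−p)^15 + 15·p·(1−p)^14
- Stop at 0 only: P(X = 0) = (1−p)^15

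At p = 0.05, (0.95)^15 = 0.4633 and 15 × 0.05 × (0.95)^14 = 0.3658, which sum to 0.8290.

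| True CBR | Printed Pr(Futility) | P(X ≤ 1) | P(X = 0) | P(X = 1), the disputed result |
|---|---|---|---|---|
| 5% | 83% | 82.9% | 46.3% | 36.6% |
| 10% | 55% | 54.9% | 20.6% | 34.3% |
| 15% | 32% | 31.9% | 8.7% | 23.1% |
| 20% | 17% | 16.7% | 3.5% | 13.2% |
| 25% | 8% | 8.0% | 1.3% | 6.7% |
| 30% | 4% | 3.5% | 0.5% | 3.1% |
| 35% | 1% | 1.4% | 0.2% | 1.3% |

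Stopping at 0 or 1 gives all seven printed values after rounding to whole percents. Stopping at 0 only gives none of them.

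**Step 2: reproduce the final-analysis columns.** For a final threshold r of 35, with stopping at X ≤ s,

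P = Σ over x > s of P(X = x) × P(Y ≥ r − x), where Y is binomial with n = 20 and the same p.

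With s = 1 and p = 0.20, r = 6, 7 and 9 give 67.2%, 53.8% and 25.0%, against the printed 67%, 54% and 25%. All 21 entries agree after rounding. With s = 0, the r = 6 column becomes 0.7, 12.9, 42.5, 72.1, 89.7, 97.0 and 99.3%, against the printed <1, 11, 39, 67, 86, 95 and 98%. Table 3 was therefore computed with stopping at 0 or 1, and SAP 18 is the outlier.

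**Step 3: what SAP 18 does with 1 of 15.** 1/15 = 6.667%.

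| Reading of SAP 18 | Outcome at 1 of 15 |
|---|---|
| Printed sign with the printed fraction: 1/15 ≥ 1/15 | Go |
| Rate rounded to one decimal: 6.7% ≥ 6.7% | Go |
| Unrounded rate against 6.7%: 6.667% < 6.7% | No-Go |
| Lead-in wording (must exceed the target, or fall below the reference) with the fraction | Neither |

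Only the third reading agrees with SAP 5. The gloss of under 7% in SAP 5 and Protocol 10.6 does include 1/15, so those texts are consistent with their own counts.

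**Step 4: expected cohort size.** E(N) = 15 + 20 × (1 − P(stop)).

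| True CBR | Stop at 0 or 1 | Stop at 0 only | Difference |
|---|---|---|---|
| 5% | 15 + 20 × 0.1710 = 18.4 | 15 + 20 × 0.5367 = 25.7 | 7.3 |
| 10% | 15 + 20 × 0.4510 = 24.0 | 15 + 20 × 0.7941 = 30.9 | 6.9 |
| 15% | 15 + 20 × 0.6814 = 28.6 | 15 + 20 × 0.9126 = 33.3 | 4.6 |
| 20% | 15 + 20 × 0.8329 = 31.7 | 15 + 20 × 0.9648 = 34.3 | 2.6 |

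**Step 5: effect on the final analysis.** The largest change in any Table 3 probability is 72.1 − 67.2 = 4.9 points (6 or more of 35, true CBR 20%). At a true CBR of 5% the same probability moves from 0.6% to 0.7%.

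**The case against.** The best defence is that SAP 18 makes no new rule. It refers back to what was already noted and sends the reader to Table 3, whose footnote is explicit. Three clear count statements stand against one loose percentage that defers to them. The section's lead-in speaks of exceeding the target, which 1/15 does not do, and the unrounded rate falls just under 6.7%. On this view SAP 18 is ambiguous at 1 of 15 rather than wrong, and the extra subjects arise only if someone reads it in isolation.

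Much of this stands. The consequences are conditional on a literal reading, and the documents do show what was meant. The rounding convention in SAP 7.4, "All percentages will be rounded to one decimal place (ie, XX.X" percent), concerns how summaries are reported, so it cannot by itself fix how a decision rule is applied. Nor does the precedence clause in SAP 1 settle a conflict inside the SAP. It only means that Protocol 10.6 cannot be assumed to override SAP 18.

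The conflict remains. The section's explicit definition is the greater-than-or-equal sign beside the fraction 1/15, and that makes 1 of 15 a Go without any rounding argument. The strict lead-in does not restore the stop either: 1/15 is not below 1/15, so under that reading the result is unclassified. The pointer to Table 3 is a reason to correct the sentence, since it disagrees with its own source.

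**Conclusion.** The concern holds. The inequality in SAP 18 gives the wrong outcome for 1 of 15, and the plan's own operating characteristics identify 0 or 1 of 15 as the intended stopping set. The error is confined to that one statement: SAP 5, Table 3 and Protocol 10.6 agree, and the printed probabilities are correct.

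If SAP 18 were applied as printed, a cohort with a true CBR of 5% to 10% would be about 34 to 37 percentage points less likely to stop, and its expected size would rise by about 7 subjects. That rise is an upper figure: under SAP 4.1.2 the Safety Review Committee decides on expansion, and under SAP 5 a tumor type taken into Part 2B does not expand. The figures assume independent outcomes, 15 evaluable subjects at the interim, and 35 after every Go. Final-analysis probabilities change by at most 4.9 points. The sentence should be corrected before the gate is used, but the design itself is sound on this point.

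**What to change.** Replace the target and reference values in SAP 18 with counts, and delete both 6.7% values:

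> *No-Go if 0 or 1 of the 15 Stage 1 subjects has clinical benefit; Go if at least 2 of the 15 do (2/15 = 13.3%).*

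Reword the lead-in to match, so that it no longer speaks of exceeding one value or falling below another. Keep the reference to Table 3.

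The cost is a wording change in one SAP section. Table 3, SAP 5, the sample size and the protocol stay as they are, and the SAP 19 statement of no changes then holds for this rule.

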## **19. CHANGES FROM PROTOCOL-STATED ANALYSES**

There are no changes from the protocol-stated analyses.

## **21. APPENDICES**

[\*\*Appendix A:\*\*](#) Schedule of Events for Screening and Cycles 1 & 2

[\*\*Appendix B:\*\*](#) Schedule of Events for Cycle 3+

[\*\*Appendix C :\*\*](#) Tumor Marker Reference Ranges

## APPENDIX A. SCHEDULE OF EVENTS FOR SCREENING AND CYCLES 1 & 2

Study Period	Screening a	Pre-Treatment (Baseline)	Treatment Period										Treatment Period										
			Cycle 1 q					Cycle 2 q					Cycle 1 q					Cycle 2 q					
Cycle	Day	D-28 to D-1	D0 to D1	D1	D2	D3 t	D5 t	D8	D15	D16	D22	D28 p	D1 p	D2	D3 t	D5 t	D8	D15	D16	D22	D28 p		
Visit Window (days)						+1	+1	±1	±3			±3	+3	+1			+1	+1	±1	±3		±3	+3
Informed consent form		X																					
Inclusion/exclusion criteria		X																					
Hepatitis B and C testing		X																					
Medical history		X																					
ECOG PS		X	X											X	X							X	
Physical examination b		X	X					X	X			X	X	X				X	X		X	X	
Slit lamp exam and visual acuity s		X												X	X							X	
Pregnancy test c		X	X											X	X							X	
Vital sign measurement and oxygen saturation d		X	X	X	X			X	X	X	X	X	X	X	X			X	X	X	X	X	
12-lead ECG e		X	X	X	X			X	X	X			X	X	X			X	X	X	X	X	
Hematology (Protocol Table 8)		X	X					X	X			X	X	X				X	X		X	X	
Serum chemistry (fasting) g (Protocol Table 9)		X	X					X	X			X	X	X				X	X		X	X	
HgbA1c r			X																				
Coagulation parameters g (Protocol Table 10)		X												X	X							X	
Urinalysis h		X												X	X							X	
PSA i			X											X	X							X	
Tumor markers j		X												X	X							X	

Study Period	Screening a	Pre-Treatment (Baseline)	Treatment Period										Treatment Period											
			Cycle 1 q										Cycle 2 q											
Cycle	D-28 to D-1	D0 to D1	D1	D2	D3 t	D5 t	D8	D15	D16	D22	D28 p	D1 p	D2	D3 t	D5 t	D8	D15	D16	D22	D28 p				
Day							+1	+1	+1	+3					+1		+1	+1	+1	+3				
Visit Window (days)																								
Tumor imaging and measurements k	X																						X	
PK l																								
Part 1			X	X	X	X	X	X	X						X	X	X	X	X	X	X			
Part 2			X	X			X	X																
Pharmacodynamic & biological studies m			X	X			X	X	X			X	X										X	
Circulating tumor DNA n			X									X	X										X	
Tumor biopsy or submission of tumor specimen f		X																					X	
KZR-261 treatment o			X				X	X				X							X	X				
Concomitant medications		X	X	X			X	X	X	X	X	X	X	X				X	X	X	X	X		
AE and SAEs	X																							

AEs collected through 30 days after last KZR-261 dose.

Abbreviations: AE=adverse event; aPTT=activated partial thromboplastin time;  $\beta$ -hCG= $\beta$ -human chorionic gonadotropin; CA=cancer antigen; CEA=carcinoembryonic antigen; CT=computed tomography; DNA=deoxyribonucleic acid; ECG=electrocardiogram; ECOG PS=Eastern Cooperative Oncology Group Performance Status; EOT=End of Treatment; INR=internal normalized ratio; mCRPC=metastatic castration-resistant prostate cancer; MRI=magnetic resonance imaging; PBMC=peripheral blood mononuclear cell; PCWG3= Prostate Cancer Working Group 3; PD= progressive disease; PK=pharmacokinetics; PSA=prostate-specific antigen; PT=prothrombin time; PTT=partial thromboplastin time; RECIST=Response Evaluation Criteria in Solid Tumors; RNA=ribonucleic acid; SAE=serious adverse event; WOCBP=woman of childbearing potential

a All Screening procedures must be performed prior to the Day 0 or Day 1 visit. Eligibility for this study should be assessed only after signing of informed consent.

b A complete physical examination including measurement of body weight will be conducted at Screening and Baseline. Height will be measured at the Screening visit only. An abbreviated physical examination including measurement of body weight will be conducted at all other study visits indicated. Subjects with skin, subcutaneous, or lymph node metastases may also have tumor evaluations (including measurements, with a ruler or calipers) by means of physical examination. Patients will be asked at each visit about mouth dryness and salivary gland pain and sensitivity, and urinary and ejaculation issues.

c For WOCBP, a negative serum  $\beta$ -hCG pregnancy test is required at Screening and a negative pregnancy test, serum or urine, at all other visits indicated. The Screening visit test should be performed within 2 weeks prior to treatment and in closer proximity to treatment start date if required by local/institutional regulations. A positive urine pregnancy test result should be confirmed by a serum pregnancy test. Pregnancy testing may occur more frequently if required by local/institutional regulations.

d Vital signs and oxygen saturation will be measured at all visits except Days 3 and 5. Blood pressure and pulse should be measured after the subject has had at least 5 minutes of rest in the seated position. If blood pressure is elevated on the first measurement at Screening or Baseline, it should be repeated after an additional 5 minutes of rest. It is recommended that blood pressure be obtained from the same arm at each assessment.

e When performed at the same time point, vital sign measurements should be performed per institutional guidelines, preferably prior to ECGs. A 12-lead ECG is performed 10 minutes after the subject has been in the supine position. ECGs will be performed on Days 1 and 15 of Cycles 1 and 2 pre-treatment, 15 minutes after the start of the infusion, at the end of the infusion, and 5 and 30 minutes, and 2, 4, 6, and 24 hours (Day 2 and Day 16) post-infusion. Additional ECGs will be performed on Day 8, 30 minutes prior to infusion, and 5 and 15 minutes and 1-hour post-infusion. ECG time points during the infusion, at the end of the infusion, and  $\leq 1$  hour post-infusion have a  $\pm 2$  minute window. ECG time points  $> 1$  hour post-infusion have a  $\pm 5$  minute window; the 24-hour ECG has a  $\pm 60$  minute window.

f Tumor biopsies (fresh [preferred] or archived) will be requested pre-treatment. Although a fresh sample is preferred, submission of an adequate tumor specimen (paraffin block) collected within one year before the subject's first dose of KZR-261 will be acceptable for subjects where a fresh sample cannot be obtained. If a paraffin block is not available, a minimum of 10 and up to 20 5- $\mu$ m unstained slides should be provided. For any subject who provided a tumor sample pre-treatment, an additional biopsy of accessible tumor will be requested at either the end of Cycle 2 (Days 21-28 of Cycle 2) or at PD, whichever comes first. Pre-treatment tumor biopsies (fresh only) will be required for subjects enrolled in the All-Tumors expansion cohort (exceptions to this requirement may be considered after discussion with the Medical Monitor); an additional biopsy of accessible tumor tissue will be required at either the end of Cycle 2 (Days 21-28 of Cycle 2) or at PD, whichever comes first. Blood samples for coagulation parameter tests must be collected within 24 hours prior to all biopsy procedures.

g Blood samples for serum chemistry tests must be collected with subject in a fasting state (ie, no food or caloric drinks for at least 6 hours before testing, or overnight). For coagulation parameter tests, either PT or INR may be measured, and either PTT or aPTT, depending on institutional standards. Blood samples for coagulation parameter tests must be collected within 24 hours prior to all biopsy procedures. It is recommended that the smallest appropriate sampling tubes be used for sample collection to curtail blood loss due to phlebotomy.

h Urinalysis dipstick testing is acceptable.

i Only subjects with mCRPC.

j If tumor markers in blood (eg, PSA, CA-125, CEA, CA-15.3, CA-19.9) are known to be elevated, they should be measured.

k All subjects must have Baseline imaging (CT scan of chest/abdomen/pelvis or MRI, as indicated) within 28 days prior to first dose of study treatment. Imaging should be repeated prior to Cycle 3 (ie, end of Cycle 2). There is a 7-day window around imaging procedures to allow time for result availability prior to the next cycle. If an imaging procedure must be scheduled to occur outside the 7-day window allowance, this should be discussed with the Medical Monitor for approval prior to the procedure. Response assessments will be conducted in accordance with RECIST 1.1 criteria. Subjects with mCRPC will be assessed per PCWG3 guidelines. All subjects with mCRPC will have bone scans at the same time points as the imaging procedures. Subjects with skin, subcutaneous, or lymph node metastases may also have tumor evaluations (including measurements, with a ruler or calipers) by means of physical examination.

l Plasma PK samples will be collected during Part 1 on Days 1 and 15 of Cycles 1 and 2 pre-treatment, 15 minutes post-start of infusion, end of infusion, 5 minutes, 15 minutes, 30 minutes, 1 hour, 2 hours, 4 hours, 6 hours, and 24 hours (ie, Day 2 and Day 16) post-infusion. An additional plasma sample will be obtained in Cycles 1 and 2 at 48 hours (Day 3) and 96 hours (Day 5) post-infusion and on Day 8 at pre-treatment (30 minutes prior to infusion), 15 minutes and 1 hour after completion of the infusion.

Plasma PK samples will be collected during Parts 2A and 2B on Day 1 of Cycle 1 at the end of infusion and 24 hours post-start of infusion (Day 2). An additional plasma sample will be obtained on Days 8 and 15 prior to infusion and Day 15 at the end of infusion.

Windows for PK sampling are provided in the laboratory manual.

m Whole blood samples will be collected for pharmacodynamic studies Cycle 1 Day 1 pre-treatment, 6 hours post-dose, 24 hours post-dose (Day 2), Cycle 1 Day 8 pre-treatment and Cycle 1 Day 15 pre-treatment, 6 hours post-dose, 24 hours post-dose (Day 16), and Cycle 2 Day 1 pre-treatment in a [REDACTED] tube for RNAseq, in sodium heparin to be shipped to central laboratory for PBMC processing, and in sodium heparin processed onsite to plasma samples (as described in the laboratory manual). Samples will be collected on Cycle 1 Day 28 if treatment is halted and not proceeding to Cycle 2.

n Whole blood will be collected in a [REDACTED] tube and shipped to the central laboratory for processing to plasma samples (for circulating tumor DNA testing) and cell pellet (cellular genomic DNA) pre-treatment Day 1 of Cycle 1, pre-treatment Day 1 Cycle 2, or at time of disease progression.

o Subjects should remain at the study site for 6 hours following study treatment administration for observation for the first cycle, first dose (Cycle 1 Day 1) and for 2 hours for the rest of Cycle 1 dosing (Cycle 1 Days 8 and 15). For Cycle 2, subjects will be under observation for 1 hour following study treatment administration. For Cycle 3 and beyond, there will be no required monitoring following study treatment administration.

p Day 28 assessments of the prior cycle may be combined with Day 1 of the next cycle. Whenever possible, these evaluations should be referred to as the End of Cycle evaluation (for the earlier cycle) as opposed to the beginning of cycle evaluation for the subsequent cycle.

q For subjects who discontinue study treatment during or after Cycles 1 or 2, see EOT evaluations in [Appendix B](#). Subsequent to discontinuation of study treatment, subjects will have an EOT visit as soon as possible following their last KZR-261 dose and prior to initiation of follow-on anticancer therapy. Safety follow-up by telephone will occur approximately 30 days following their last KZR-261 dose. Subjects who discontinue study treatment for reasons other than PD will be contacted by telephone approximately every 90 days for 12 months after last study treatment for evidence of PD, collection of information about subsequent anti-tumor therapy, and assessment of survival status. Subjects who discontinue study treatment for PD will be contacted by telephone approximately every 90 days for 12 months after last study treatment for assessment of survival status.

r HgbA1c to be measured at pre-treatment (baseline).

s Subjects will have monitoring for cataracts at Screening, at the end of Cycle 1 prior to the start of Cycle 2, and at the end of Cycle 2 prior to Cycle 3.

t Day 3 and Day 5 visits are for Part 1 only.

